11.3.2. Reporting Serious Adverse Events

In the event of an SAE, regardless of suspected causality, the Investigator must notify the Sponsor and/or its safety representative immediately, without undue delay, and under no circumstances later than 24 hours of becoming aware of the event using study specific SAE forms. The Investigator must provide detailed follow-up AE information, as necessary, to the Sponsor and/or its safety representative in a timely manner to meet regulatory reporting requirements. Serious AEs must also be reported to the Independent Ethics Committee/Institutional Review Board according to their policies and procedures.

Study Number: SLN360-002	Compound No.: SLN360
Protocol	Version: 1.0

Recruitment episodes, complications or progression of the initial SAE must be reported as follow-up to the original episode immediately, without undue delay, under no circumstances later than 24 hours of the Investigator receiving the follow-up information. An SAE occurring at a different time interval or otherwise considered completely unrelated to a previous reported one should be reported separately as a new event.

If an Investigator becomes aware of an SAE occurring after discontinuation but he or she considers it to be related to study drug, the Investigator should report the event to the Sponsor.

11.4. Follow-up of Adverse Events

For the purposes of this study, the period of observation for collection of AEs extends from the time the patients provide informed consent until the last follow-up visit. Follow-up of the AE, even after the date of therapy discontinuation, is required if the AE persists until the event resolves or stabilises at a level acceptable to the Investigator.

Every reasonable effort will be made to follow up with patients who have AEs. Any patient who has an ongoing AE that is related to the IMP or study procedures at the follow-up visit will be followed up, where possible, until resolution, or until the unresolved AE is judged by the Investigator (or designee) to have stabilised. This will be completed at the Investigator's (or designee's) discretion. Any patient who has an ongoing AE that is not related to the IMP or study procedures at the follow-up visit can be closed out as ongoing at the Investigator's and Sponsor's discretion.

Any SAE that is not resolved by the end of the study or upon discontinuation of the patient's participation in the study is to be followed up until it either resolves, stabilises, returns to randomisation values (if a randomisation value is available) or is shown to not be attributable to the study drug or procedures.

11.5. Pregnancy

If the outcome of the pregnancy meets the criteria for immediate classification as an SAE (e.g., postpartum complications, spontaneous miscarriage, still birth, or congenital anomaly [even of an aborted foetus]), the Investigator should follow the procedures for reporting an SAE ([Sections 6.5.7](#) and [11.3.2](#)). Note, elective termination of a pregnancy would not meet the criteria for an SAE, and in these cases, a follow-up pregnancy report should be provided by the Investigator.

12. DATA ANALYSIS AND STATISTICAL CONSIDERATIONS

The database will be locked and the main analysis will be performed after all participants have completed 36 weeks of treatment. All follow-up data collected up to Week 60 will be analysed subsequently and included in the final report.

Study Number: SLN360-002	Compound No.: SLN360
Protocol	Version: 1.0

Prior to the database lock (either at main or final analysis), a detailed, finalised Statistical Analysis Plan (SAP) will be completed, approved and placed on file. The SAP will contain a more comprehensive description of the statistical analyses methodology for the study than outlined in this Protocol. The SAP will provide full details of the analyses, the data displays and the algorithms to be used for data derivations, database closure and unblinding of the randomisation code. The SAP will also contain the rules and data handling conventions that will be used to perform the analyses and the procedure(s) that will be used to account for missing data. Any change to the analysis methods described in the Protocol will be documented in the SAP and/or Clinical Study Report (CSR) along with the justification for making the change. Additional exploratory analyses performed after the database lock that are not described in the SAP can be conducted as deemed appropriate. These additional analyses will be fully identified as exploratory post-hoc analyses in the CSR.

12.1. Hypotheses

To demonstrate the treatment effect of SLN360 compared with placebo, the following hypothesis:

$$H0: \mu T = \mu P$$

will, at the 5% significance level, be tested against the alternative hypothesis:

$$H1: \mu T > \mu P$$

wherein μ denotes the mean time-averaged change in Lp(a) from baseline to Week 36, T denotes SLN360 and P denotes placebo. For estimating treatment effects, the difference between treatments and corresponding confidence intervals will be provided.

12.2. Estimands

12.2.1. Primary Estimand

The primary estimand for this study is defined by the following attributes:

- Target population: participants with elevated Lp(a) at high risk of ASCVD events
- Treatments: SLN360 versus placebo
- Primary outcome measure: time-averaged change in Lp(a) from baseline to Week 36
- Analysis set and handling of intercurrent events: All available values of Lp(a) will be included in the calculation of time-averaged change from baseline in Lp(a)
- Population level summary: difference in mean time-averaged change in Lp(a) from baseline to Week 36 between treatment groups

Study Number: SLN360-002	Compound No.: SLN360
Protocol	Version: 1.0

Further details will be included in the SAP.

12.2.2. Secondary Estimands

Secondary estimands, if used, will be specified in the SAP.

12.3. Study Design Considerations

12.3.1. Sample Size Assumptions

A total of five treatment groups and approximately 160 participants are planned. Each placebo group will include 20 randomly allocated participants, and each SLN360 group will include 40 randomly allocated participants. This will result in a total of 120 participants exposed to SLN360 and 40 participants exposed to placebo. The placebo groups will be analysed and reported both separately and in combination.

The treatment effect observed in the FIH Phase 1 study (APOLLO; ClinicalTrials.gov identifier NCT04606602; EudraCT identifier 2020-002471-35) between placebo and 300 mg SLN360 at Day 150 (the smallest effect observed at the lowest dose to be used in the proposed study) was approximately 60% with a conservative pooled standard deviation of 40%. As few as 10 participants per arm would give approximately 90% power to detect this magnitude of difference, at the 5% significance level ($p < 0.05$).

The proposed sample size, even separating the placebo arms with a different dose frequency, is expected to be more than adequate to demonstrate the SLN360 effect on Lp(a). The larger sample size should allow a more robust evaluation of safety at these doses and dose frequencies than a smaller sample size that may be expected in a Phase 2 study.

12.3.2. Sample Size Sensitivity

The sensitivity of the sample size will not be investigated because 40 participants per active arm are planned and as few as 10 participants per arm would provide adequate power.

12.3.3. Sample Size Re-estimation

No sample size re-estimation will occur during the study.

12.4. Data Analysis Considerations

Analysis of variance methodology will be used to test for differences between active treatment and placebo for the primary endpoint of time-averaged change from baseline in Lp(a) and secondary endpoints including time-averaged, percent and absolute change

Study Number: SLN360-002	Compound No.: SLN360
Protocol	Version: 1.0

from baseline in Lp(a) and other lipids/lipoproteins including LDL-C, total cholesterol and apoB. Multiplicity adjustment to the type 1 error will be applied for comparisons of active treatment arms versus placebo with similar dosing regimens and will be described in the SAP. Pairwise comparisons between active arms will be considered exploratory and multiplicity adjustments will not be applied.

The distribution of Lp(a) is expected to be positively skewed, but the percentage change from baseline Lp(a) value is not expected to have the same distribution; therefore, parametric testing is appropriate. Testing the assumption of normality will be performed before any formal analysis and sensitivity analyses will be undertaken, if required. Full details of this process will be included in the SAP.

Baseline will be defined as last non-missing observation/measurement before the start of study drug administration.

Descriptive statistics will be used to summarise safety and PD endpoints by treatment group.

Each SLN360 dosing regimen will be presented separately.

12.4.1. Analysis Populations

The following analysis populations will be included for this study:

- Screened Population: all participants who signed an ICF
- Safety Population: all participants who received at least one dose of study drug
- Pharmacodynamic Population: all participants who received at least one dose of study drug and have evaluable PD data

12.4.2. Treatment Comparisons

Treatment comparisons will be made between the active treatment arms and the placebo arms.

12.4.3. Interim Analysis

There will not be a formal interim data analysis. The main analysis will be performed after all participants have completed 36 weeks of treatment. All follow-up data collected up to Week 60 will also be analysed and reported.

Study Number: SLN360-002	Compound No.: SLN360
Protocol	Version: 1.0

12.4.4. Key Elements of Analysis Plan

12.4.4.1. Efficacy Analyses

12.4.4.1.1. Primary endpoint

Analysis of variance methodology will be used to test for differences between active treatment and placebo for time-averaged change in serum Lp(a) for the PD population. Individual and mean and/or median Lp(a) will also be presented graphically as per each scheduled visit by treatment group.

12.4.4.1.2. Secondary endpoints

Pharmacodynamic biomarker data will be listed and summarised using analysis of variance techniques based on the PD Population. Individual and mean and/or median PD biomarkers will also be presented graphically as per each scheduled visit by treatment group.

12.4.4.2. Safety Analyses

Safety and tolerability will be evaluated in the Safety Population by means of AE reports, physical examination findings, 12-lead ECGs, vital signs and laboratory safety evaluations. Safety parameters will be listed and summarised using descriptive statistics. No formal statistical hypothesis testing is planned for safety data.

Descriptive statistics of vital signs, 12-lead ECGs and safety laboratory evaluations at each visit will be presented by treatment group. The changes from baseline will be similarly presented. Physical examination findings will be listed.

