- A serum pregnancy test is required at screening. Urine pregnancy testing will be performed at other timepoints
- On dosing days, vital signs should be performed pre-dose and at 5 minutes and 1 hour post-dose

Study Number: SLN360-002
Protocol

Study Number: SLN360-002				Compound No.: SLN360	
Protocol				Version: Final Version	

Procedure	Screening		Intervention Period						Follow-up Period	EoS	
	Optional Pre-screening	Screening	8	12	16	20	24	28	32	36	
Week	-6	-4	0	1	4	8	12	16	20	24	40
Day	-	-	1	8	29	57	85	113	141	169	197
Window (days)	-	-	-	±1	±2	±3	±3	±4	±6	±7	±8
									±9	±10	±12
										±12	±14

f. On dosing days, 12-lead ECG should be performed pre- and 1 hour (+/- 30mins) post-dose.

g. A list of safety laboratory parameters is presented in Section 6.5.6. Note that the full set of parameters listed may not be assessed at every timepoint

h. On dosing days, blood samples for PD biomarkers should be collected pre-dose. Note that the full set of parameters listed in Section 6.4 may not be assessed at every timepoint. If an optional pre-screening visit is conducted only Lp(a) is to be measured at that visit

Note: Participants may stay at sites overnight on the night before and/or after a visit if required.

Study Number: SLN360-002
Protocol

Compound No.: SLN360
Version: Final Version

15.2. Appendix: Time and Events Table – Groups 2, 4 and 5 (Dosing Every 24 Weeks)

Procedure	Optional Pre-screening	Screening	Intervention Period												Follow-up Period	EoS	
			Week -6	-4	0	1	4	8	12	16	20	24	28	32	36		
Week	-6																
Day	-	-			1	8	29	57	85	113	141	169	197	225	252	281	337
Window (days)	-	-			-	-	±1	±2	±3	±3	±4	±6	±7	±8	±9	±10	±12
Informed consent	X	X															
Eligibility assessment	X ^a	X															
Viral serology	X																
Demography	X																
Medical history	X																
Lifestyle & dietary restrictions	X	X															
Physical examination ^b	X	X	X	X	X	X	X	X	X	X	X	X	X	X	X	X	
Concomitant/ prior medication	X	X	X	X	X	X	X	X	X	X	X	X	X	X	X	X	
Randomisation	X																
Dose administration	X																
SARS-CoV-2 testing ^c	X	X	X	X	X	X	X	X	X	X	X	X	X	X	X	X	
Pregnancy testing ^d	X	X	X	X	X	X	X	X	X	X	X	X	X	X	X	X	
Vital signs	X	X	X	X	X	X	X	X	X	X	X	X	X	X	X	X	

Study Number: SLN360-002
Protocol

Compound No.: SLN360
Version: Final Version

Study Number: SLN360-002		Intervention Period										Follow-up Period		EoS							
Procedure	Optional Pre-screening	Screening										Intervention Period									

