3.5.3 Vital Signs

Vital signs will include systolic and diastolic blood pressure, heart rate, temperature and respiratory rate. Descriptive statistics will be provided for vital sign values as well as change from baseline at each scheduled visit.

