3.5.4 Electrocardiograms

For the continuous variables, descriptive statistics of results at each study visit, as well as the change from baseline to each study visit, will be presented in summary tables; for the categorical responses to overall interpretation (rhythm), results and the associated findings at each visit will be summarized by counts and percentages.

Number and percentage of patients with QTcF interval in the categories below will be provided.

- Absolute QTcF interval >500 msec,
- Absolute QT interval >500 msec,
- Increase from baseline QTcF interval >60 msec.

A shift table from baseline to scheduled post-baseline will be tabulated for overall interpretation (rhythm).

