3.5.5 Injection Site Assessments

The number and percentage of subjects will be presented for any pain, tenderness, erythema/redness, and induration/swelling of injection site location at each visit and time point.

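### Post-dose vital signs and ECGs at the second and third doses are referenced to a baseline 16 to 32 weeks old; the same-day pre-dose value is collected and would be a cleaner reference

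*Protocol*

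**What the plan says.** The dosing-day footnotes to the Time and Events tables (Protocol 15.1, repeated in 15.2) set the readings. For vital signs: "On dosing days, vital signs should be performed pre-dose and at 5 minutes and 1 hour post-dose". For ECGs: "On dosing days, 12-lead ECG should be performed pre- and 1 hour (+/- 30mins) post-dose". Group 3 is dosed at Weeks 0, 16 and 32, and Groups 4 and 5 at Weeks 0 and 24. The placebo groups follow the same two schedules (Protocol 4.1.1).

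Protocol 12.4.4.2 sets the summaries: "Descriptive statistics of vital signs, 12-lead ECGs and safety laboratory evaluations at each visit will be presented by treatment group". It adds: "The changes from baseline will be similarly presented". Protocol 12.4 defines the reference: "Baseline will be defined as last non-missing observation/measurement before the start of study drug administration". SAP 3.1.3 ties baseline explicitly to the first dose, so there is one baseline per participant and none per dose.

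SAP 3.5.3 says of vital signs: "Descriptive statistics will be provided for vital sign values as well as change from baseline at each scheduled visit". SAP 3.5.4 plans for ECGs "descriptive statistics of results at each study visit, as well as the change from baseline to each study visit", and adds counts for QTcF above 500 msec, QT above 500 msec and a QTcF rise above 60 msec, plus a rhythm shift table. SAP 3.5.5, on injection sites, does go down to the reading within the visit: "induration/swelling of injection site location at each visit and time point". SAP 3.5 places all safety data in listings.

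**The concern.** A reading 5 minutes or 1 hour after an injection is most informative when set against the reading taken just before that injection. On Day 1 the plan does this, because the last pre-dose value is the baseline. At later doses it does not: the reference stays at Day 1, although a fresh pre-dose value is taken on the same day. Whatever has moved over the intervening months, such as background medication or ordinary visit-to-visit variation, enters the reported change alongside any acute effect.

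Vital signs and ECGs are named components of the secondary safety endpoint (Protocol 3.2.1), and the sample size is justified partly by a more robust safety evaluation (Protocol 12.3.1). What is at stake is how clearly the tables can show acute tolerability on repeat dosing.

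**Working it through.** The documents give no precision, power or SD for vital signs or ECGs, so there is no stated figure to reproduce. The comparison below rests on assumed SDs.

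**Age of the reference value**
- Q16W: second dose at Week 16, third at Week 32; gaps to baseline of 16 and 32 weeks.
- Q24W: second dose at Week 24; gap of 24 weeks.
- With the same-day pre-dose value, the gap falls within one visit day.

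**What the within-group change contains**

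Let the acute effect be 5 units and let drift common to all groups be −5, 0 or +5.

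| Common drift | SLN360 change from Day 1 | Placebo change from Day 1 | Difference | SLN360 change from same-day pre-dose |
|---|---|---|---|---|
| −5 | 0 | −5 | 5 | 5 |
| 0 | 5 | 0 | 5 | 5 |
| +5 | 10 | +5 | 5 | 5 |

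Within the SLN360 group, one acute effect can read as 0, 5 or 10. The difference from placebo recovers 5 when drift is common. If SLN360 has extra drift g of its own, the difference reads 5 + g, while the same-day change still reads 5.

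**Noise**

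Inputs: n = 40 per SLN360 group (Protocol 12.3.1); assumed systolic between-visit SD Sv = 6 to 10 mmHg; assumed reading SD Sr = 5 to 7 mmHg; t quantile on 39 df = 2.023.

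- SD of change against Day 1 = √(2(Sv² + Sr²))
- SD of change against same-day pre-dose = √(2Sr²), because the visit component cancels
- 95% half-width = 2.023 × SD / √40

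Low end (Sv = 6, Sr = 5):
- Day 1: √(2 × 61) = 11.05; half-width 3.5 mmHg
- Same day: √50 = 7.07; half-width 2.3 mmHg

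High end (Sv = 10, Sr = 7):
- Day 1: √(2 × 149) = 17.26; half-width 5.5 mmHg
- Same day: √98 = 9.90; half-width 3.2 mmHg

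**Cross-check with a different parameterisation**

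Take a total SD of 10 units, a same-day correlation of 0.8 to 0.9 and a long-interval correlation of 0.4 to 0.7 (all assumed), with SD of change = 10√(2(1 − r)).
- Against Day 1: 7.7 to 11.0
- Against same-day pre-dose: 4.5 to 6.3
- Ratio: 1.2 to 2.4, in favour of the same-day reference throughout

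**The case against.** The strongest reply is that the trial is randomised and placebo-controlled on matching schedules. Drift common to all groups cancels in expectation when SLN360 is read beside placebo, and results are shown by treatment group. This stands, and it rules out the stronger inference that acute change cannot be separated from drift. The same-day pre-dose values are also collected and listed, so the contrast can be built. But these sections plan group-wise descriptive statistics and no between-group difference, and neither the added noise nor SLN360-specific drift is removed by placebo.

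Second, a reader might infer that pre-dose and post-dose readings are averaged under one visit label. That would shrink a Day 1 effect to two-thirds for vital signs present at both post-dose times, (0 + x + x)/3, and to one-half for ECGs, (0 + x)/2. No section says so. SAP 3.1.2 assigns safety data to nominal CRF visits and is silent on several readings within one visit, and SAP 7 leaves programming detail to a separate document. If tables are run by time point, Day 1 dilution is zero. For the same reason no claim can be made that intervals would be too narrow from treating repeated readings as independent.

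Third, by-visit means are not the only output. The QT/QTcF categories, rhythm shift table, listings and adverse event tables offer other routes to detection. That is correct, although the category for a QTcF rise above 60 msec also uses the Day 1 baseline.

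Finally, these are descriptive data with no formal test, so the primary result is untouched. That also stands.

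**Conclusion.** The point holds for the reference value at doses 2 and 3. Even if programmers tabulate by time point, post-dose readings at Weeks 16, 24 and 32 are compared with a value 16 to 32 weeks old, and neither document defines a change from the same-day pre-dose value. Under the assumed SDs, this costs roughly 1.2 to 2.3 mmHg in the systolic 95% half-width at n = 40 (3.5 − 2.3 at the low end, 5.5 − 3.2 at the high end). The size depends on SDs and correlations that the documents do not give; the direction holds whenever readings on one day correlate more closely than readings months apart.

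Dilution of a Day 1 effect is possible but not stated, and is not part of the conclusion. The absence of a time-point level in SAP 3.5.3 and 3.5.4 is missing detail, worth closing in the same edit. Overall this is a cheap improvement to a descriptive safety analysis, not an error that threatens the trial's conclusions.

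**What to change.** Add to SAP 3.5.3 and 3.5.4:

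> On dosing days, vital signs and ECG results will be summarised by visit and time point. Post-dose values will be presented as change from the same-day pre-dose value, by treatment group and dose number, in addition to change from the Day 1 baseline. All post-dose ECGs count for the QT/QTcF categories.

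Keeping both references lets slow drift (pre-dose value against Day 1) be read apart from acute change (post-dose against same-day pre-dose). Protocol 12 already leaves full analysis detail to the SAP, and the planned change from baseline is retained, so no Protocol change is needed. The cost is SAP wording and a few more table rows, with no new data or procedures; the downside is slightly longer safety tables.

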12.4.4.2.1. Adverse events

The verbatim terms used in the eCRF by Investigators to identify AEs will be coded using MedDRA. All reported AEs with onset during the treatment phase will be included in the analysis and will be summarised by treatment group, and these include the following: AEs that have worsened since study entry, TEAEs, study drug-related TEAEs, serious TEAEs, study drug-related serious TEAEs, TEAEs leading to study discontinuation, TEAEs leading to discontinuation of study treatment or TEAEs leading to death. All other AEs will be listed only.

For each AE, the number and percentage of participants who experience at least one occurrence of the given event will be summarised by treatment group. Summaries will be presented overall and also by system organ class and preferred term using MedDRA. TEAEs will also be summarised by severity and relationship classified by System Organ Class and Preferred Term.

Study Number: SLN360-002	Compound No.: SLN360
Protocol	Version: 1.0

The number and percentage of early withdrawals and the corresponding reasons will be tabulated presenting number and percentage of participants for each treatment group.

Summaries, listings, datasets or narratives may be provided, as appropriate, for those participants who die, discontinue treatment due to an AE or experience a severe or serious AE.

